4.2 Selection of Additional Covariates

The covariates selected for cohorts 1-3 primary model will be used in all cohort 4 analytical models.

4.3 Primary Efficacy Analysis

For all estimands intercurrent events will be accounted for as described in the main SAP.

4.3.1 Primary Efficacy Estimand

The primary efficacy estimand will be the effect of cohort 4 EDP1815 compared to the cohort 4 matched placebo group on the percentage of participants achieving EASI-50 at Week 16. The population summary measure of interest will be the odds ratio between active EDP1815 treatment group and matched placebo.

4.3.2 Main Analytical Approach

The primary analysis will be performed using a logistic regression model as described in the main SAP.

Treatment will consist of 4 levels (cohort 4 placebo, matched placebo from cohorts 1-3, cohort 4 EDP1815 and cohort 1 EDP1815). Baseline vIGA will consist of 3 levels (2, 3 and 4).

The following treatment differences will be of estimated:

- Cohort 4 EDP1815 vs Cohort 4 matched placebo
- Cohort 4 EDP1815 vs Cohort 1 EDP1815*
- Cohort 4 EDP1815 vs Cohort 4 placebo**

* Comparisons between cohort 4 EDP1815 and cohort 1 EDP1815 will be considered as exploratory analysis.

** Comparisons between cohort 4 EDP1815 and cohort 4 placebo will be considered as sensitivity analysis.

P-values will be only displayed for the comparison of active treatment vs placebo groups.

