11.4. Planned Analyses

For all Cohort 1-3 analyses, data for the relevant endpoint will be analyzed within the same model and the Cohort 1-3 placebo groups will be pooled.

For all Cohort 4 analyses, the Cohort 4 EDP1815 data will be compared to the Cohort 4 Matched Placebo data. In separate models for the primary and selected secondary endpoints, the Cohort 1 EDP1815 data will be added to the model and compared to the Cohort 4 EDP1815 data; these analyses will be considered as exploratory.

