11.8. Determination of Sample Size

Cohorts 1-3

The sample size was calculated using the assumption that data from the placebo participants in the three cohorts can be pooled prior to comparison with the EDP1815 treatment groups. No adjustments for multiple testing have been made.

The primary efficacy endpoint is the achievement of EASI-50 at Week 16. The pooled placebo response rate is estimated to be approximately 25% and a doubling of this to 50% for EDP1815 would be considered as clinically meaningful.

Using a two-sided test at the 5% level of significance, 58 participants in each treatment group would give 80% power to detect a difference in one of the EDP1815 cohorts compared to the pooled placebo group. There would also be more than 90% power to compare the pooled EDP1815 6.4×10^{11} daily dose or all the EDP1815 group to the pooled placebo group.

Under the assumption of a 20% drop-out of participants prior to Week 16 this will require a total of at least 73 participants to be enrolled in each treatment group. In order to allow for the 3:1 randomization in each cohort this has been adjusted to 75 participants per treatment group to give a total of 300 participants recruited. With 75 EDP1815 participants and 25 placebo participants in each of the three cohorts.

Cohort 4

Using the same assumptions relating to the placebo rate, clinically meaningful difference, significance level, and drop-out rate as above for Cohorts 1-3, approximately 70 participants are required in each of the EDP1815 8.0×10^{10} and Cohort 4 Matched Placebo groups to provide approximately 80% power in detecting a difference between EDP1815 and placebo in Cohort 4.

In order to allow 50% of the placebo control group to be concurrent controls and 50% to be historic matched controls from Cohorts 1-3, a 2:1 randomization will be used to enroll 70 EDP1815 8.0×10^{10} subjects and 35 placebo participants to Cohort 4.

If sensitivity analyses indicate that pooling of the Cohort 4 placebo group with the Cohort 1-3 matched placebo data is inappropriate, then the power of the comparison between the Cohort 4

EDP1815 and placebo groups is approximately 65% if only Cohort 4 placebo participants could be used in the treatment comparisons.

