4.1 Pooling of Placebo Cohorts

For cohort 4 efficacy analyses, cohort 4 placebo group and set of 35 matched placebo participants from cohorts 1-3 will be pooled into a single 'cohort 4 matched placebo' group and will be used as a common control group for the cohort 4 EDP1815 treatment group.

As a sensitivity analysis, the cohort 4 EDP1815 treatment group will also be compared to the cohort 4 placebo group in all relevant analyses.

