4.4 Secondary Efficacy Analyses

The following treatment differences will be estimated:

- Cohort 4 EDP1815 vs Cohort 4 matched placebo
- Cohort 4 EDP1815 vs Cohort 4 placebo
- Cohort 4 EDP1815 vs Cohort 1 EDP1815 *

* Comparisons between cohort 4 EDP1815 and cohort 1 EDP1815 will be considered as exploratory analysis.

Treatment will consist of 4 levels (cohort 4 placebo, matched placebo from cohorts 1-3, cohort 4 EDP1815 and cohort 1 EDP1815).

The comparison with pooled placebo groups (cohort 4 matched placebo) will be done using contrasts (LSMESTIMATE statement) within the relevant SAS procedures.

For other information see the main study SAP.

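### The Cohort 4 primary model splits the placebo group and adds Cohort 1 EDP1815, so it does not estimate the odds ratio against the single pooled Matched Placebo group that the plan defines

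*SAP*

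**What the plan says.** **One pooled control, Cohort 1 kept apart.**
- Protocol 11.2 limits the Cohort 4 analysis tables, and all primary and secondary comparisons, to two groups: EDP1815 8.0x10^10 and the Cohort 4 Matched Placebo.
- Protocol 11.4 says: "In separate models for the primary and selected secondary endpoints, the Cohort 1 EDP1815 data will be added to the model". It calls those analyses exploratory, and Protocol 11.3.2 and 11.4.5 agree.
- Addendum 4.1 says the Cohort 4 placebo group and the 35 matched placebo participants from Cohorts 1-3 "will be pooled into a single" group that serves as the common control. Addendum 4.3.1 defines the primary odds ratio against that group.

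**Four treatment levels.**
- Addendum 4.3.2, the primary analysis model, says: "Treatment will consist of 4 levels (cohort 4 placebo, matched placebo from cohorts 1-3, cohort 4 EDP1815 and cohort 1 EDP1815".
- Addendum 4.4 repeats the four levels for secondary endpoints and adds: "The comparison with pooled placebo groups (cohort 4 matched placebo) will be done using contrasts (LSMESTIMATE statement". It gives no weights.
- For the primary endpoint, 4.3.2 refers to the main SAP. Section 9.3.3 there uses LSMESTIMATE for pooled active groups and active-versus-active comparisons, and carries the pooled Cohorts 1-3 placebo as a single level.

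**Declared changes.** The Addendum's table of changes (Section 6) has two entries: the new Bayesian prior and the added comparison with Cohort 4 placebo alone. The main SAP's table (Section 13) does not mention a four-level model either.

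**The concern.** The pooled group named in Addendum 4.1 and 4.3.1 is not a level of the model in 4.3.2. The comparison with it has to be assembled from two placebo levels, and an average of two logits is not the logit of the pooled proportion. The primary Cohort 4 estimate therefore targets something other than the odds ratio the plan defines, and it depends on weights nobody has written down. The gap opens when the two placebo sets respond differently. The Addendum itself records doubt about their similarity as its reason for adding the Cohort 4-only comparison. Giving the later document precedence does not resolve this, because Addendum 4.1 and 4.3.1 conflict with Addendum 4.3.2.

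**Working it through.** **Inputs (Protocol 11.8).** "Using a two-sided test at the 5% level of significance, 58 participants in each treatment group would give 80% power". "The pooled placebo response rate is estimated to be approximately 25% and a doubling of this to 50% for EDP1815". "Under the assumption of a 20% drop-out of participants prior to Week 16". For Cohort 4, "a 2:1 randomization will be used to enroll 70 EDP1815" participants and 35 placebo, plus about 35 borrowed placebo. After 20% drop-out, 70 becomes 56 and 35 becomes 28.

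**1. The plan's own figures.** The standard two-proportion formula for 25% against 50% gives 58 per group, and 58/0.8 = 72.5, rounded up to 73, as stated. For Cohort 4, with unpooled variance:
- 56 v 56: z = 0.25/√(0.25/56 + 0.1875/56) = 2.828; power = Φ(2.828 − 1.960) = 80.7% (stated: about 80%).
- 56 v 28: z = 0.25/√(0.25/56 + 0.1875/28) = 2.366; power = Φ(0.406) = 65.8% (stated: about 65%).

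The stated 80% therefore fits a two-group comparison with one pooled control.

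**2. Closed form.** Let A be the log odds ratio against the pooled group and B the equal-weight contrast over two placebo levels of equal size.
- A = logit(p_active) − logit((p1 + p2)/2)
- B = logit(p_active) − [logit(p1) + logit(p2)]/2

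With p_active = 50% (logit 0) and pooled placebo 25%:

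| Placebo sets | OR under A | OR under B |
|---|---|---|
| 25/25% | 3.00 | 3.00 |
| 20/30% | 3.00 | 3.06 |
| 15/35% | 3.00 | 3.24 |
| 10/40% | 3.00 | 3.67 |

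At 15/35% the logits are −1.735 and −0.619, their mean is −1.177, and exp(1.177) = 3.24. The logit is concave below 50%, so averaging logits lowers the control log-odds and raises the odds ratio.

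**3. A data set that crosses 0.05 (unadjusted).** Active 23/56; placebo 3/28 and 11/28 (14/56 pooled).
- A: ln(23/33) − ln(14/42) = 0.738, OR 2.09. SE = √(1/23 + 1/33 + 1/14 + 1/42) = 0.411. 95% CI 0.93 to 4.68, p = 0.073.
- B: −0.361 − (−2.120 − 0.435)/2 = 0.917, OR 2.50. SE = √[1/23 + 1/33 + ¼(1/3 + 1/25 + 1/11 + 1/17)] = 0.452. 95% CI 1.03 to 6.07, p = 0.043.

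**4. The weights matter.** Active 24/56; placebo 3/24 and 11/32. The OR is 2.25 pooled, 2.74 with equal weights, and 2.50 with weights proportional to n.

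**5. How often it matters.** Exact enumeration, unadjusted, 56/28/28, excluding the at most about 1% of outcomes with an empty cell:

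| True placebo / active | Median B/A ratio of ORs (5-95%) | p<0.05 under A | p<0.05 under B | Verdicts differ |
|---|---|---|---|---|
| 25/25% / 50% | 1.01 (1.00-1.12) | 78.0% | 79.2% | 1.3% |
| 15/35% / 50% | 1.08 (1.00-1.46) | 78.1% | 82.4% | 4.4% |
| 25/25% / 25% | 1.01 (1.00-1.12) | 4.5% | 4.8% | 0.6% |
| 15/35% / 25% | 1.08 (1.00-1.46) | 4.1% | 4.4% | 1.7% |

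Covariate-adjusted simulations (vIGA and EASI effects assumed; 60 evaluable Cohort 1 EDP1815 participants, which is 80% of 75) gave verdict disagreement of 2.3% to 3% at equal placebo rates. With the two sets at 15% and 35%, in either order, disagreement was 3.9% to 5.5%.

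**6. The Cohort 1 part.** In simulation with both placebo sets at 25% and active at 50%, the median OR was 3.13 for the two-level model and 3.09 with a pooled control plus Cohort 1 EDP1815. It was 3.18 for the four-level model.

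**The case against.** **Only one model is written out.** A reader might infer that the analyst has two documented primary odds ratios to choose from after unblinding. The documents do not support that. Addendum 4.3.2 is the only place where the Cohort 4 treatment levels are specified; 4.1 and 4.3.1 name a control group and a summary measure. One can also read them together, with the pooled control formed by a contrast as in 4.4. What remains is that such a contrast is a different quantity from the one 4.3.1 defines. It is stated for the Cohort 4 pooled placebo only under secondary endpoints, and its weights are open.

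**The split is partly visible.** The change table lists the Cohort 4-only placebo comparison, which needs separate placebo levels if run in the same model. Main SAP Section 8 lists Cohort 4 Placebo and Cohort 1 EDP1815 as columns in Cohort 4 efficacy outputs. This is fair, but an added sensitivity comparison and a display column do not declare a change to the primary control, and nothing declares Cohort 1's entry into the primary model.

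**The effect is small.** This stands. A typical shift in the odds ratio is about 1% when the placebo sets are alike, against a standard error of roughly 0.41 on the log scale. The 10/40% split is a tail case. The null rows above show no type I error inflation, and the study states an estimation focus without multiplicity adjustment.

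**Separate placebo levels are defensible.** Given the doubt about similarity, this is reasonable for a sensitivity analysis. It does not make the result the primary odds ratio as defined.

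**Conclusion.** The inconsistency is real, and the sponsor should correct it. Following Addendum 4.3.2 does not estimate the odds ratio defined in 4.3.1 and in the protocol, and the change table does not say so. The effect is usually modest: an odds ratio of 3.24 against 3.00 at 15/35%, with verdict disagreement of about 1-3% at equal true placebo rates and about 4-6% at 15/35%. With placebo rates below 50% and equal weights, the split tends to give the larger odds ratio as the two sets diverge.

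Two stronger statements should be avoided. Including Cohort 1 EDP1815 does not materially distort the result; nearly all of the difference comes from splitting the placebo. Nor do the two forms agree whenever observed placebo rates are equal: with 6/24, 8/32 and active 24/56, both give OR 2.25, but p is 0.048 pooled and 0.049 with equal weights.

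The figures assume equal contrast weights except where noted, 28 evaluable participants in each placebo set, the response rates shown and, for the adjusted runs, assumed covariate effects and 60 evaluable in Cohort 1.

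**What to change.** In Addendum 4.3.2, fit the primary comparison with a two-level treatment factor: Cohort 4 EDP1815 and the pooled Cohort 4 Matched Placebo, as in Protocol 11.2 and 11.4 and Addendum 4.1. Make the same change in 4.4. Use one separate model for the sensitivity comparison with Cohort 4 placebo alone and another for the exploratory comparison with Cohort 1 EDP1815. If the four-level model is kept for any comparison, label it sensitivity or exploratory, state the weights on the two placebo levels, and enter it in the Addendum's table of changes before Cohort 4 is unblinded. The cost is Addendum wording and two extra model runs; no new data are needed.

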4.3.3 Cohort 4 Specific Sensitivity Analyses

4.3.3.1 Within Cohort 4 Analysis

Comparison between cohort 4 EDP1815 and cohort 4 placebo will be considered a sensitivity analysis for the primary endpoint. Primary analysis approach will be used.

4.3.3.2 Bayesian sensitivity analysis

A sensitivity analysis on the primary endpoint will be performed using Bayesian dynamic borrowing via robust mixture priors. The analysis will incorporate all Cohort 4 data and Cohort 1-3 placebo data.

Robust mixture priors utilize historical data (in this case, Cohort 1-3 placebo data) to supplement concurrent data (Cohort 4 placebo data). In contrast to other methods, this method is more robust due to the inclusion of a weakly informative component in the prior distribution. The inclusion of this component allows for dynamic borrowing, increasing borrowing from historical data which is similar to the concurrent data, and decreasing borrowing in the event of prior-data conflict (Heinz Schmidli 2014).

The analysis model will be constructed as follows. Let y_0 , y_1 , and y_2 be the number of EASI-50 responses at Week 16 observed in Cohorts 1-3 placebo, Cohort 4 placebo, and Cohort 4 EDP1815 groups. Similarly, denote N_0 , N_1 , and N_2 as the number of patients with a Week 16 observation, per the Primary Estimand definition. The likelihood functions for the Cohort 4 Active and Cohort 4 placebo groups are:

$$y_1 \sim \text{Bin}(N_1, \pi_1)$$

$$y_2 \sim \text{Bin}(N_2, \pi_2)$$

The prior distribution for the Cohort 4 EDP1815 response rate is the weakly informative prior:

$$\pi_2 \sim \text{Beta}(1,1)$$

The prior distribution for the Cohort 4 placebo group response rate is based on a robust mixture of an informative component, based on the data observed in Cohorts 1-3 placebo group, and a weakly informative component:

$$\pi_1 \sim (1 - w)\text{Beta}(y_0, N_0 - y_0) + w\text{Beta}(1,1)$$

Here w is the a priori weight on the weakly informative component of the prior. Based on a simulation study, the weight will be set to .5 to adequately control Type 1 error and provide adequate power.

Posterior distributions will be calculated using the RBest package in R. The following summary statistics will be calculated based on the posterior distributions:

- Posterior means, standard deviations and 95% credible intervals for π_1 , π_2 , and $\pi_2 - \pi_1$
- Posterior probability $\Pr(\pi_2 - \pi_1 > 0)$
- Approximate number of Cohort 1-3 patients borrowed for the analysis

The approximate number of patients borrowed will be calculated based on the difference of ESS of the π_1 posterior and number patients in the Cohort 4 placebo group: $ESS - N_1$. ESS will be calculated based on the Elir method (Beat Neuenschwander 2020).

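### ESS minus N1 is not a valid count of Cohort 1-3 placebo patients borrowed: it is +2 when none are, and about zero or negative under strong placebo conflict while borrowing continues

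*SAP*

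**What the plan says.** SAP Addendum 4.3.3.2 gives the Cohort 4 placebo response rate π1 a two-component prior, (1-w)Beta(y0, N0-y0) + w Beta(1,1). The first component carries the Cohort 1-3 placebo data. On w, the addendum states that "the weight will be set to .5 to adequately control Type 1 error and provide adequate power".

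The listed outputs are posterior means, standard deviations and 95% credible intervals for π1, π2 and π2-π1, the posterior probability that π2-π1 exceeds zero, and "Approximate number of Cohort 1-3 patients borrowed for the analysis". On that last item the addendum says: "The approximate number of patients borrowed will be calculated based on the difference of ESS of the" π1 posterior and N1, that is, ESS minus N1, and "ESS will be calculated based on the Elir method". The same section defines N0, N1 and N2 "as the number of patients with a Week 16 observation, per the Primary Estimand definition".

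The section makes no allowance for the Beta(1,1) prior inside the ESS and does not say how to read a value at or below zero. The posterior mixture weight is not a listed output.

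**The concern.** After the update, π1 has a two-component posterior: one component combines Cohort 1-3 and Cohort 4 placebo data, the other uses Cohort 4 placebo data with a flat prior. When the two placebo groups disagree strongly, both components can keep weight while sitting apart. The mixture is then wider than the Cohort 4 data alone would give, so its ESS can fall below N1 while Cohort 1-3 data still influence the estimate. When conflict is extreme and the Cohort 1-3 component drops out, the ESS returns to N1 plus the two pseudo-observations of the flat prior.

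The figure is meant to tell a reader how far the result leaned on non-concurrent controls. Section 6 of the addendum records doubt about whether the two placebo groups are alike, and Protocol 11.8 considers what follows "If sensitivity analyses indicate that pooling of the Cohort 4 placebo group with the Cohort 1-3 matched placebo data is inappropriate". A figure near zero, or a negative number of patients, could be read as no reliance on Cohorts 1-3 when there is some.

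**Working it through.** **Inputs.** The plan states no value for the number borrowed, so there is none to reproduce. The sizes come from Protocol 11.8.

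- Cohort 1-3 placebo: "With 75 EDP1815 participants and 25 placebo participants in each of the three cohorts", so 3 × 25 = 75 randomised. With the planned 20% drop-out, N0 = 75 × 0.8 = 60. (The same allowance reproduces the plan's own step: 58/0.8 = 72.5, rounded up to 73.)
- Cohort 4 placebo: "35 placebo participants to Cohort 4", so N1 = 35 × 0.8 = 28.
- Planned placebo rate 25%, so y0 = 0.25 × 60 = 15 (assumed as the observed value).
- w = 0.5.
- y1, the Cohort 4 placebo responders, is not in the documents and is varied.

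**No borrowing.** The posterior is Beta(a, b) with a = 1+y1 and b = 1+N1-y1. The ELIR ESS is the posterior expectation of -[d²log p(θ)/dθ²] × θ(1-θ). For a Beta this is (a-1)E[(1-θ)/θ] + (b-1)E[θ/(1-θ)] = b + a = N1+2 (for 1 ≤ y1 ≤ N1-1). The rule therefore reports N1+2-N1 = +2 with nothing borrowed. This needs no assumption about results.

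**With borrowing.** The posterior weight on the Cohort 1-3 component is

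w* = (1-w)L0 / [(1-w)L0 + wL1], with L0 = B(y0+y1, N0-y0+N1-y1)/B(y0, N0-y0) and L1 = B(1+y1, 1+N1-y1).

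The posterior mean is w*(y0+y1)/(N0+N1) + (1-w*)(1+y1)/(N1+2). The no-borrowing mean (w = 1) is (1+y1)/(N1+2). The ELIR ESS of the mixture was obtained by numerical integration; Beta(20,40) returns 60.0, as it should.

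Example, 13/28: w* = 0.318, and the mean is 0.318 × 28/88 + 0.682 × 14/30 = 41.95%, against 14/30 = 46.67% without borrowing, a shift of -4.7 points.

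| y1 of 28 | Gap to 25% (points) | w* | ESS - N1 | Mean, no borrowing | Mean, mixture | Shift (points) |
|---|---|---|---|---|---|---|
| 1 | -21.4 | 0.20 | -2.4 | 6.7% | 9.0% | +2.3 |
| 7 | 0.0 | 0.80 | +39.4 | 26.7% | 25.3% | -1.3 |
| 10 | +10.7 | 0.68 | +24.8 | 36.7% | 31.1% | -5.6 |
| 11 | +14.3 | 0.58 | +15.9 | 40.0% | 33.9% | -6.1 |
| 12 | +17.9 | 0.46 | +7.0 | 43.3% | 37.6% | -5.8 |
| 13 | +21.4 | 0.32 | +0.2 | 46.7% | 42.0% | -4.7 |
| 14 | +25.0 | 0.19 | -3.1 | 50.0% | 46.7% | -3.3 |
| 15 | +28.6 | 0.10 | -3.2 | 53.3% | 51.4% | -1.9 |
| 16 | +32.1 | 0.045 | -1.7 | 56.7% | 55.7% | -1.0 |
| 17 | +35.7 | 0.018 | -0.1 | 60.0% | 59.6% | -0.4 |
| 20 | +46.4 | 0.001 | +1.8 | 70.0% | 70.0% | 0.0 |

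The measure is not monotone. It reads +0.2 at 13/28, with a 4.7-point shift, and +1.8 at 20/28, with none.

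**Robustness.** With no drop-out (N0 = 75, y0 = 19, N1 = 35), 16, 17 and 18 responders give -1.7, -4.6 and -4.4, with shifts of -4.1, -2.8 and -1.7 points; 2/35 gives -3.3 with +2.4 points. Cohort 1-3 placebo rates of 15%, 35%, 40% and 45% show the same pattern. A moment-based ESS is also negative at 13, 14 and 15 of 28 (-6.9, -7.3, -5.9), so ELIR is not the cause.

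**How likely.** From Binomial(28, p), the chance of 13 to 17 responders, where the rule reports about zero or less, is 1.1%, 4.9%, 14.1%, 29.7%, 48.1% and 62.2% for true Cohort 4 placebo rates of 25%, 30%, 35%, 40%, 45% and 50%.

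**The case against.** The best defence is that the figure works over much of the range and matters little where it does not. At upward gaps of 11 to 18 points it is +25, +16 and +7, falling as conflict grows, as intended. The failure needs a gap of roughly 21 to 29 points (Fisher p = 0.053, 0.028 and 0.015 at 13, 14 and 15 of 28), and 25 points is the whole design effect. At 16 or 17 responders the shift is 1 point or less, so a value near zero is nearly right. At the planned 25% rate, 13 to 17 responders would be seen about 1% of the time. All of this stands and sets the size of the point.

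A second defence is that a negative value reports something real: at 14/28 the posterior SD is 0.107, against 0.090 without borrowing, so the mixture has lost precision. That also stands. It rules out the weight times N0 as a substitute effective sample size, since 0.19 × 60 ≈ 11 would present a loss of information as patients gained. But it supports the ESS difference only as a precision measure, not as a number of patients borrowed.

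Third, other outputs help. The posterior mean of π1 is listed, the Cohort 4-only placebo group has its own summary column (Protocol 11.2, SAP section 8), and EDP1815 against Cohort 4 placebo alone is a planned sensitivity analysis (Addendum 4.1 and 4.3.3.1). A careful reader could recover much of the shift, so the count is not the only evidence on reliance. None of this makes the count itself correct.

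**Conclusion.** The concern holds as a defect in one descriptive output. As defined, the number borrowed is +2 when nothing is borrowed. It is about zero or negative at placebo gaps of about 21 to 29 points, where Cohort 1-3 data still move the placebo mean by about 2 to 5 points. The +2 is exact; the other figures rest on N0 = 60, y0 = 15, N1 = 28 and assumed values of y1.

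A reader might infer more, but the documents do not support it:

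- That the Bayesian result is wrong. The posterior means, intervals and probability of benefit do not use the count.
- That a decision depends on the count. Protocol 11.8 gives a conditional power statement with no threshold and no mention of ESS.
- That the hidden pull always favours EDP1815. It does when Cohort 4 placebo responds better than Cohorts 1-3, but at 1/28 the measure is -2.4 while the placebo estimate is raised by 2.3 points.
- That N1 has two definitions. Its later description as the size of the Cohort 4 placebo group is loose, but the symbol is already defined by Week 16 observations, and the formula uses the symbol.

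**What to change.** In Addendum 4.3.3.2, make two quantities the measure of borrowing: the posterior weight on the Cohort 1-3 component, and the shift in the posterior means of π1 and π2-π1 against the same model with w = 1. Both are needed: at 7/28 the weight is 0.80 but the shift is only 1.3 points, because the groups agree. Since π2 has its own prior, the shift in π2-π1 is equal and opposite to that in π1.

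If the ESS difference is kept, compute it as ESS - (N1+2). At 7, 13, 14, 15 and 20 of 28 this gives +37.4, -1.8, -5.1, -5.2 and -0.2. Label it a change in effective information, and state that values at or below zero can signal conflict between the placebo groups and do not mean that nothing was borrowed.

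The cost is a wording change, a few lines of R and one or two more reported figures. The weight is a by-product of the planned update, and no new data are needed.
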